## **Statistical Analysis Plan**

## Primary Outcome

The primary outcome of the study is the feasibility of the protocol as defined as ≥80% of participants completing the 8-week protocol. It will be measured by percentage completed the 8-week protocol. If more than or equal to 80% of participants complete the 8-week protocol it will be deemed feasible. Rates of completion will also be compared by treatment arm at the Week 8 time point. Adherence to the study protocol will also be measured as attendance to telerehab sessions and ≥80% attendance will be defined as adherent. Percentage deemed adherent will be compared between the treatment arms at the 8-week time point.

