## **Hypotheses**

We hypothesize that:

 The telerehabilitation protocol will demonstrate sufficient feasibility (defined as ≥80% of participants completing the 8-week protocol) to support a larger, multisite randomized controlled trial.

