## Intervention groups

Active Rehab - outpatient rehabilitation delivered via synchronous, video-based telerehabilitation for 8 weeks; PTs, OTs and/or SLPs (depending on clinical need), twice per week for 50-minute sessions (for each discipline of clinical need) during Radiation Therapy (up to 8 weeks). Neurosurgeon or oncologist may also refer outpatient rehab through the Toronto Rehab

- ABI Day Hospital after Radiation Therapy if a participant meets the Toronto Rehab ABI Day Hospital acceptance criteria
- 2. Usual Care generic aerobic and strengthening exercise instructions and an 8-week subscription to BrainHQ during Radiation Therapy; Neurosurgeon or oncologist may also refer outpatient rehab through the Toronto Rehab ABI Day Hospital after Radiation Therapy if a participant meets the Toronto Rehab ABI Day Hospital acceptance criteria

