## Outcome Measurements

## **Primary Outcome**

The primary outcome is feasibility of the intervention as measured by the percentage of participants who complete the intervention at week 8.

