## **Study Sample Size and Statistical Analysis Sample Size**

A sample of 54 participants, 27 per arm, is planned for this study based upon an expected recruitment rate of a third (33%) of glioma patients seen in recruiting clinics (163 patient per annum). Feasibility trials are recommended to recruit between 20 to 50 participants per arm to adequately investigate if a protocol is feasible or not and a minimum of 22 participants per arm is required for precision

of the variance estimation. Loss to follow-up (LOF) will be analyzed as the primary outcome and the sample size will not be adjusted for LOF.

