## **Documenting participant withdrawal**

In all circumstances, reasons for withdrawal will be collected and all participants will be followed through to the trial's conclusion with previously stated outcome measures performed (timing is outlined in Table 1), as the main analysis will be an intention to treat analysis. This will, of course, be subject to the participant's continued consent to return for these assessments. Participants who withdraw consent will be advised to follow up with their regular health care provider.

Participants who are withdrawn or withdraw from active treatment will not be replaced.

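### The 80% feasibility rule is not restricted to the telerehabilitation arm it is meant to judge, and the sample size section names a different primary outcome (loss to follow-up)

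*Protocol*

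**What the plan says.** The Hypotheses section ties the 80% criterion to the intervention: "The telerehabilitation protocol will demonstrate sufficient feasibility", enough to support a larger multisite trial. Under Outcome Measurements, the primary outcome is "feasibility of the intervention as measured by the percentage of participants who complete the intervention at week 8".

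The Statistical Analysis Plan section (Primary Outcome) turns this into a decision rule: "If more than or equal to 80% of participants complete the 8-week protocol it will be deemed feasible". The next sentence adds a comparison of completion rates between arms at week 8, with no threshold for either arm.

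The Sample Size section plans 54 participants, 27 per arm, and explains the lack of any inflation for attrition with the statement "Loss to follow-up (LOF) will be analyzed as the primary outcome". Under Secondary Outcomes, follow-up rates are already listed separately, as Retention. Under Documenting participant withdrawal, "reasons for withdrawal will be collected and all participants will be followed through" to the end of the trial, subject to consent.

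Usual care during radiation consists of generic exercise instructions and a BrainHQ subscription (Intervention groups). The protocol does not define what counts as completing in either arm. The 80% attendance rule defines adherence to telerehabilitation sessions, not completion.

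**The concern.** This rule is the only stated criterion for judging the protocol feasible, and two of its elements are not fixed.

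**Denominator.** The hypothesis is about telerehabilitation, but the rule counts participants without naming an arm. If usual care is included, its completion rate can lift a telerehabilitation arm that falls short of 80% over the line, or pull one that meets 80% below it. Completing usual care does not show that patients can complete scheduled video therapy during radiation.

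**Quantity.** Completing the intervention and remaining in follow-up are different events. A participant who stops telerehabilitation in week 2 but attends the week 8 evaluation is a non-completer under the Outcome Measurements definition, yet is not lost to follow-up under the Sample Size sentence. The two versions of the primary outcome can therefore give different verdicts on the same data.

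**Working it through.** **Inputs from the protocol.** "A sample of 54 participants, 27 per arm, is planned for this study"; threshold at least 80%; 1:1 allocation. The protocol gives no expected completion rate for either arm, so the true rates below are assumptions, shown over a range.

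**The plan's own figure.** The sample size rests on an "expected recruitment rate of a third (33%) of glioma patients seen in recruiting clinics (163 patient per annum"). 163 × 0.33 = 53.8 and 163 / 3 = 54.3, so 54 is reproduced. No power calculation is stated, so there is none to check.

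**Pass marks.**
- Pooled: 0.80 × 54 = 43.2, so 44 completers are needed. 44/54 = 81.5% passes and 43/54 = 79.6% fails.
- Telerehabilitation arm only: 0.80 × 27 = 21.6, so 22 are needed. 22/27 = 81.5% passes and 21/27 = 77.8% fails.

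**Smallest telerehabilitation count that passes the pooled rule** (44 minus usual-care completers):

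| Usual-care completers | Telerehabilitation completers needed | Telerehabilitation completion |
|---|---|---|
| 24/27 (88.9%) | 20 | 74.1% |
| 25/27 (92.6%) | 19 | 70.4% |
| 26/27 (96.3%) | 18 | 66.7% |
| 27/27 (100%) | 17 | 63.0% |

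**Probability of passing.** Let p1 and p2 be true completion in telerehabilitation and usual care, with 27 per arm and independent outcomes.
- Pooled: sum over a = 0 to 27 of Bin(a; 27, p1) × P(Bin(27, p2) ≥ 44 − a).
- Arm only: P(Bin(27, p1) ≥ 22).

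| p1 (assumed) | p2 = 80% | p2 = 85% | p2 = 90% | p2 = 95% | Arm only |
|---|---|---|---|---|---|
| 65% | 9% | 17% | 29% | 47% | 5% |
| 70% | 17% | 30% | 47% | 66% | 14% |

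In the other direction, p1 = 85% and p2 = 70% gives 30% pooled against 79% arm only.

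**Precision at the pass mark (Clopper-Pearson 95%).** 44/54: 69% to 91%, half-width about 11 points. 22/27: 62% to 94%, half-width about 16 points.

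**The two versions of the primary outcome.** The Hypotheses and Statistical Analysis Plan sections speak of completing the 8-week protocol, and Outcome Measurements of completing the intervention at week 8. These are close to each other. Loss to follow-up in the Sample Size section is the one that differs: the withdrawal section keeps people who stop treatment under assessment, and Secondary Outcomes already treats follow-up as a separate measure.

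**The case against.** The best defence is that the protocol never says both arms are combined. The Hypotheses and Outcome Measurements sections can be read as confining the 80% criterion to telerehabilitation. That is correct, and it limits the claim: pooling is the plain reading of the rule, because the arm comparison is introduced as an addition, but it is not an explicit statement. The defence does not remove the problem, since the denominator of the rule is then left open between 27 and 54.

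A second defence is that a pilot also asks whether the larger randomised trial can be run, and usual-care completion bears on that. This stands. It is a reason to report usual-care completion and retention, but not to let them decide whether telerehabilitation is feasible. Because rates by arm will be reported, a weak telerehabilitation arm would be visible, although no threshold would apply to it.

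Some stronger readings are tempting but not supported:
- That 63% is a typical passing result. It needs all 27 usual-care participants to complete.
- That the error always favours telerehabilitation. It reverses when usual care completes less often.
- That there are three conflicting definitions. Only the loss-to-follow-up sentence names a clearly different quantity.
- That the protocol contradicts itself on the length of the course. The words "during Radiation Therapy (up to 8 weeks") can be read as the length of radiation, and the same paragraph gives eight weeks of telerehabilitation, as does the Telerehab Intervention Protocol section. At most the wording could be clarified.

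The absence of a stated interval for the primary outcome is minor by itself, since that is commonly left to a separate analysis plan.

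**Conclusion.** The concern holds in this form: the feasibility rule does not say that it applies to the telerehabilitation arm and plainly read includes usual care, and the Sample Size section names a conflicting primary outcome. A separate analysis plan could not settle this without overriding one protocol section or another.

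On the pooled reading, telerehabilitation can pass below its own 80% mark whenever at least 23 of 27 usual-care participants complete (44 − 23 = 21, and 21/27 = 77.8%). The pass-count results need only 27 per arm. The pass probabilities also depend on assumed completion rates: at 65% true telerehabilitation completion, the chance of a positive verdict is about 2 to 9 times that of an arm-only rule (9% to 47% against 5%) over usual-care completion of 80% to 95%. If the sponsor always meant the telerehabilitation arm alone, these false passes do not arise, but the text still has to say so.

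**What to change.** 1. In Hypotheses, Outcome Measurements and the Statistical Analysis Plan section, state one primary outcome: the proportion of all participants randomised to telerehabilitation who complete it to week 8, with stopping for any reason counted as non-completion. Compare it with 80% (22 of 27 if 27 are randomised) and report an exact 95% confidence interval.
2. Give one definition of completion, distinct from the attendance-based adherence rule.
3. In Sample Size, delete the statement that loss to follow-up is the primary outcome. Keep follow-up in both arms under Retention.
4. Report usual-care completion and retention separately, as evidence on running the larger trial, without a pooled verdict.

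The cost is wording only, with no added participants or data collection. The price is precision: with 27 rather than 54 in the denominator, the interval at the pass mark widens from about ±11 to about ±16 points, which is the information the trial actually has on telerehabilitation.

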## Adherence to telerehab protocol:

Adherence will be monitored using the Encounters data in EPIC, which displays "no-show" data to therapy sessions were attended. >80% attendance will be considered adherence to the telerehab protocol.

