## Secondary Outcomes

Secondary outcomes (e.g. balance, mobility, quality of life, mood, etc.) are continuous in nature and will be analyzed using linear regression, adjusted for baseline. Time to all-cause mortality, time to disease specific mortality, and time to disease progression will be analyzed using Kaplan Meier estimators and logrank tests.

Disease and demographic factors that may influence protocol attrition and adherence will be analyzed using a generalized linear mixed effects model with an assumed unstructured covariance matrix structure and robust sandwich estimation.

To assess the safety of the protocol, the number, type, and severity of SA events will be reported as a cumulative incidence and compared between treatment arms using a Poisson regression.

Since these analyses are hypothesis generating, complete-case analyses will be used, p-values will not be listed and 95% confidence intervals of estimates and change scores will be used instead so the study results can be interpreted in context. The standard deviation of changes in secondary outcome measures will be used for sample size calculations for future full-scale studies.

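### Adherence is defined only as telerehab attendance but is to be compared between arms, although usual care has no telerehab sessions; the adherence cut-off and the unit for the adherence model also need tidying

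*Protocol*

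**What the plan says.** The primary outcome is completion of the 8-week protocol. Under Statistical Analysis Plan, Primary Outcome, a second measure is added: "Adherence to the study protocol will also be measured as attendance to telerehab sessions and ≥80% attendance will be defined as adherent". The next sentence reads: "Percentage deemed adherent will be compared between the treatment arms at the 8-week time point".

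Intervention groups gives synchronous telerehabilitation to the Active Rehab arm. Usual Care receives "generic aerobic and strengthening exercise instructions and an 8-week subscription to BrainHQ" during radiation. Telerehab Intervention Protocol likewise assigns the programme to participants randomised to the active group.

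The section Adherence to telerehab protocol takes attendance from no-show records and states: ">80% attendance will be considered adherence to the telerehab protocol".

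Under Outcome Measurements, Secondary Outcomes, the adherence item covers the share of rehab sessions attended, participant characteristics associated with adherence, and how many participants used BrainHQ or the exercise programme and how much. It sets no level of BrainHQ or exercise use that would count as adherent.

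Under Statistical Analysis Plan, Secondary Outcomes, factors that may influence attrition and adherence are to be analysed with a "generalized linear mixed effects model with an assumed unstructured covariance matrix structure and robust sandwich estimation". The unit of analysis (participant, visit or session) is not given.

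**The concern.** A comparison between arms needs a measure that exists in both. The stated definition of adherence depends on sessions that only one arm is offered, so the planned contrast would show which arm was offered telerehab, not how well participants kept to what they were assigned. If usual-care participants are coded as non-adherent, the table shows a large difference that is an artefact. If they are coded as missing, there is nothing to compare. Either way the statistician would have to replace a stated analysis after the data are in.

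The cut-off is written in two ways, so a participant at exactly 80% could be classified differently depending on the section used. The model for attrition and adherence is one for repeated observations, while the two outcomes as defined at week 8 give a single observation per participant.

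**Working it through.** **The plan's own figure.** Sample Size states: "A sample of 54 participants, 27 per arm, is planned for this study". The inputs are 163 glioma patients per year and a one-third (33%) recruitment rate: 163 × 0.33 = 53.8 and 163 / 3 = 54.3. Both round to 54, and 54 / 2 = 27 per arm. The figure is reproduced.

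**Between-arm adherence.** For each participant, attendance = sessions attended / sessions scheduled.
- Telerehab arm: scheduled sessions = 2 per week × 8 weeks × 1 to 3 disciplines = 16, 32 or 48. Attendance is defined.
- Usual-care arm: scheduled sessions = 0. Attendance = 0/0, which is undefined.
- If usual care is coded as non-adherent, its value is 0/27 whatever participants do. With an illustrative 22/27 in the telerehab arm, the difference is 22/27 − 0/27 = 81.5 percentage points. That is simply the telerehab arm's own rate.

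**What can be reported.** In the telerehab arm alone, an illustrative 22/27 = 81.5% has an exact (Clopper-Pearson) 95% interval of 61.9% to 93.7%. The 22 is an assumption; the protocol gives no expected adherence rate.

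**The two cut-offs.** Above 80% and at least 80% differ only if exactly 80% can occur, which requires 0.8 × N to be a whole number, so N must be a multiple of 5.
- Full schedules: 0.8 × 16 = 12.8, 0.8 × 32 = 25.6, 0.8 × 48 = 38.4. None is whole, so both cuts classify everyone alike.
- Shortened course: Intervention groups also describes sessions during radiation for up to 8 weeks. Five weeks at two per week gives 10, 20 or 30 sessions for 1, 2 or 3 disciplines, and 8/10, 16/20 and 24/30 are exactly 80%.

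**The mixed model.** Week-8 completion and 80% attendance are each one yes/no value per participant. Take a logit-normal random-intercept model with no covariates, intercept b and random-effect SD s. The marginal probability P is the average of expit(b + s·z) over a standard normal z, and the log-likelihood for 22/27 is 22·ln P + 5·ln(1 − P). For every s, some b gives P = 22/27, so the maximum is the same:

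| s | fitted b | maximised log-likelihood |
|---|---|---|
| 0 | 1.482 | −12.937472 |
| 0.5 | 1.558 | −12.937472 |
| 1 | 1.759 | −12.937472 |
| 2 | 2.373 | −12.937472 |
| 3 | 3.119 | −12.937472 |

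The data do not inform s, while the intercept depends on the value chosen for it. Adding covariates supplies no repeated observations from which to estimate a within-participant covariance. If the outcome were instead repeated over the four post-baseline visits (weeks 4, 8, 12 and 26), an unstructured matrix would have 4 × 5 / 2 = 10 parameters from at most 54 participants: heavy, but not impossible in principle.

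**The case against.** **Usual care does have adherence data.** BrainHQ and exercise use are listed under the adherence item of the secondary outcomes, so something could be compared. This does not rescue the sentence: that measure has no adherent/non-adherent threshold, and the analysis section defines adherence by telerehab attendance alone. Referral to the Day Hospital, open to both arms, does not help either. It comes after radiation, depends on acceptance criteria, and is not part of the study's telerehab programme.

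**The effect on conclusions is limited.** This stands. Adherence is a secondary outcome, the feasibility decision rests on completion, and a control value of zero would be noticed when the table is built. A reader might infer from the sentence's place under Primary Outcome that it is a headline result; the outcome list does not support that.

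**The model may be sound on another reading.** This stands in part. A reader might infer that the mixed model cannot be fitted at all or would fail to converge. The documents do not support that, because the unit of analysis is not fixed and could be settled in a separate SAP. A session-by-session matrix would need k(k + 1)/2 parameters, from 136 (k = 16) to 1,176 (k = 48), but nothing in the protocol says the model is at session level. In a mixed model, unstructured may equally describe the random effects: 1 parameter for an intercept, 3 for an intercept and slope. What remains is that, for the two week-8 outcomes as defined, the covariance is not identifiable.

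**The cut-off conflict is editorial.** Largely so: it has no effect on full 8-week schedules.

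**Conclusion.** The between-arm adherence comparison is wrong as written. It follows from the protocol's own definitions, with no numerical assumption: the control value is undefined or 0% by construction. This should be corrected, but it does not threaten the trial or its primary outcome.

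The two cut-offs do conflict in text. The consequence is minor, arising only when scheduled sessions are a multiple of 5.

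The model point holds in a limited sense. The random-effect covariance is not identifiable for week-8 completion and 80% attendance when each participant contributes one yes/no value. It would not hold for a repeated outcome, if one is intended. No particular small-sample or penalised method is required by this finding; that choice is a matter of preference.

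**What to change.** - **Statistical Analysis Plan, Primary Outcome:** delete the between-arm comparison of the percentage adherent. Report the percentage adherent at week 8 in the telerehab arm only, with an exact 95% confidence interval. Describe BrainHQ and exercise use separately, as already listed under Secondary Outcomes.
- **Adherence cut:** use one form in both Adherence to telerehab protocol and Statistical Analysis Plan, Primary Outcome.
- **Statistical Analysis Plan, Secondary Outcomes:** for week-8 completion and the 80% attendance outcome, use logistic regression without random effects, and model adherence factors in the telerehab arm only. If a repeated outcome is intended, state the unit (visit or session) to which the mixed model applies.

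The cost is wording in three places. No data collection, sample size or conduct changes, and the only analysis given up is a contrast that could not be interpreted.

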## Secondary Outcomes

Secondary outcomes (e.g. balance, mobility, quality of life, mood, etc.) are continuous in nature and will be analyzed using linear regression, adjusted for baseline. Time to all-cause mortality, time to disease specific mortality, and time to disease progression will be analyzed using Kaplan Meier estimators and logrank tests.

Disease and demographic factors that may influence protocol attrition and adherence will be analyzed using a generalized linear mixed effects model with an assumed unstructured covariance matrix structure and robust sandwich estimation.

To assess the safety of the protocol, the number, type, and severity of SA events will be reported as a cumulative incidence and compared between treatment arms using a Poisson regression.

Since these analyses are hypothesis generating, complete-case analyses will be used, p-values will not be listed and 95% confidence intervals of estimates and change scores will be used instead so the study results can be interpreted in context. The standard deviation of changes in secondary outcome measures will be used for sample size calculations for future full-scale studies.

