#### Randomization

Participants will be stratified for glioma grade (grade <3, grade=4) and then randomly assigned to the 2 intervention groups using a 1:1 allocation ratio block design. The schedule will be randomly generated using the PLAN procedure (SAS 9.4, SAS Institute, USA).

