## Missing Data

Missing data for secondary measures will be assessed for quantity and nature of missingness. As secondary analyses are hypothesis generating, whole case analysis will be used even if >5% are missing data. Although the baseline values are also required for the secondary outcome analysis, we anticipate missingness

will be extremely infrequent as REDCap will be used for data collection and missing completely at random (MCAR) so that no bias will be incurred by dropping those cases from the analysis. Participants that drop out prior to completion of protocol will be right censored for survival analyses.

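### Randomisation is stratified by glioma grade but the continuous secondary-outcome regressions adjust only for baseline, so their 95% intervals are wider than the design warrants if grade is prognostic

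*Protocol*

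**What the plan says.** Under Randomization, the protocol states: "Participants will be stratified for glioma grade (grade <3, grade=4". Allocation within those strata is 1:1 in blocks. Grade is the only stratification factor.

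In the Statistical Analysis Plan section, under Secondary Outcomes, measures such as balance, mobility and quality of life "are continuous in nature and will be analyzed using linear regression, adjusted for baseline". The Missing Data section shows that baseline here means the participant's baseline score: "Although the baseline values are also required for the secondary outcome analysis". Mortality and progression "will be analyzed using Kaplan Meier estimators and logrank tests", with no stratification named. The plan reports no p-values for these outcomes: "95% confidence intervals of estimates and change scores will be used instead so the study results can be interpreted in context".

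Grade or the stratification appears in three other places in the analysis text:

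- Descriptive Variables uses baseline balance between arms to judge how the stratification performed.
- Subgroup Analyses lists tumour grade as an exploratory factor in mixed models of the secondary measures.
- The attrition and adherence model takes disease factors as predictors, but it is not a treatment comparison.

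No section carries the stratum into a main comparison of the arms.

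**The concern.** Blocked allocation within grade keeps the arms nearly balanced on grade. Grade differences therefore contribute almost nothing to the chance variation of the treatment estimate. A regression without grade still counts the between-grade variation as residual noise. Its standard error is then too large for the design, and its nominal 95% interval covers more than 95%.

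This matters more here than it would beside a p-value, because the interval is the whole of the reported inference for these outcomes and the sample is small. The model is also a stated choice: the section names both the method and its adjustment, so this is not simply detail left for a later document.

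**Working it through.** **Inputs from the protocol.** "A sample of 54 participants, 27 per arm, is planned for this study". The number rests on an "expected recruitment rate of a third (33%) of glioma patients seen in recruiting clinics (163 patient per annum": 163 × 0.33 = 53.8 and 163 / 3 = 54.3, both rounding to 54. The stated figure reproduces. No power, effect size or SD is stated, so there is no power figure to check. The stated minimum of 22 per arm (n=44) serves as a low-n case.

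**Assumptions not in the documents.** Partial R² of grade given baseline, 0 to 0.30; 60% grade 4 (50% and 80% also tried); two strata; block size 4; baseline correlation 0.5; normal errors; complete follow-up.

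**Formula.** The baseline-only model has n-3 residual degrees of freedom and the model with grade has n-4. With the arms balanced on grade, and R² the partial R² observed in the sample:

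width ratio = sqrt[(1-R²)(n-3)/(n-4)] × t(n-4)/t(n-3)

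At n=54, sqrt(51/50) = 1.0100 and t(50)/t(51) = 2.0086/2.0076 = 1.0005, so the ratio is 1.0104 × sqrt(1-R²). It equals 1 at R² = 1 - 1/1.0104² = about 0.02.

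**Simulation.** 6,000 replicates per setting, both models fitted to the same data, n=54, 60% grade 4:

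| Assumed R² | Formula ratio | Mean width, baseline only | Mean width, with grade | Simulated ratio | Coverage, baseline only | Coverage, with grade |
|---|---|---|---|---|---|---|
| 0 | 1.010 | 1.097 | 1.098 | 1.001 | 94.8% | 94.9% |
| 0.02 | 1.000 | 1.109 | 1.099 | 0.991 | 95.6% | 95.1% |
| 0.05 | 0.985 | 1.130 | 1.100 | 0.974 | 95.4% | 95.0% |
| 0.10 | 0.959 | 1.161 | 1.100 | 0.948 | 95.3% | 94.1% |
| 0.20 | 0.904 | 1.232 | 1.098 | 0.892 | 97.1% | 95.1% |
| 0.30 | 0.845 | 1.322 | 1.100 | 0.832 | 97.8% | 94.7% |

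The formula sits about one percentage point above the simulation because it takes R² as the value observed in the sample, while the simulation fixes the population value. A factor with no effect still explains about 1/51 = 0.02 of the residual by chance, which nearly offsets the lost degree of freedom. The Monte Carlo standard error of a coverage near 95% is sqrt(0.95 × 0.05 / 6000) = 0.3 points. With grade included the model is correctly specified and its true coverage is 95%, so the 94.1% is simulation noise.

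**Robustness.** At n=44 the simulated ratios are 1.001, 0.992, 0.975, 0.949, 0.890 and 0.832. At n=54 and R² 0.10, 50% grade 4 gives 0.948 and 80% gives 0.947.

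**Where the gain comes from.** At n=54 and R² 0.10, the empirical SD of the treatment estimate is 0.281 without grade and 0.280 with it. The estimate is hardly more precise; the reported interval is brought into line with the precision it already has.

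**The case against.** The best case for leaving the text alone is that these analyses are declared hypothesis-generating, the baseline-only interval remains valid with coverage of about 95% to 98%, and the baseline score may already carry most of what grade predicts. If the partial R² is about 0.02 or less, there is essentially nothing to gain. Most items in the protocol's list of secondary outcomes under Outcome Measurements (recruitment, adherence, retention, experience, safety) are not analysed by these regressions. A separate statistical analysis plan could also add covariates. All of this limits the size and reach of the point. It does not remove the mismatch between the stated design and the stated model, and including grade costs almost nothing even where it does not help.

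A reader might infer more than the documents support:

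- **That the SD passed to the next trial is inflated.** The plan carries forward the SD of changes in the secondary measures, not a regression residual SD. Adding grade to the model leaves that SD as it was.
- **That adjustment is worth 11% to 25% more participants** (1/0.9 = 1.11 and 1/0.8 = 1.25 at partial R² of 0.10 and 0.20). Stratified allocation already delivers that precision; only the reported interval changes.
- **That the survival comparison gains at least as much.** A log-rank test gives no interval to narrow, and the documents offer no event count or hazard assumption. With 54 participants and a last visit at 26 weeks, events may be few and the gain from stratifying small.
- **That the estimates are biased, for instance through dropout related to grade.** With complete follow-up there is no bias. The documents give no dropout by grade and arm from which to show any.

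The exploratory subgroup models do use grade, but they examine grade as a factor and leave the main comparison of the arms unadjusted for it.

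**Conclusion.** The point holds as a modest loss of reported precision. The protocol stratifies by grade and then specifies a baseline-only regression, so the intervals for the continuous secondary outcomes are wider than the design warrants to the extent that grade is prognostic beyond baseline. The mismatch is certain from the text. Its size is not: it runs from nothing to about a 17% narrowing at n=54 over the assumed range, and is about 5% at a partial R² of 0.10. The error is in the conservative direction. It is confined to secondary analyses; the primary outcome, a completion percentage set against 80%, is untouched.

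**What to change.** In the Statistical Analysis Plan section, under Secondary Outcomes, add the randomisation stratum as a covariate beside the baseline value in each continuous secondary-outcome regression, or state why it is left out.

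The stratum must be defined first. Randomization names grade below 3 and grade 4, while the inclusion criteria admit any grade, so grade 3 belongs to neither stratum. Assign it there and use the same coding in the model.

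Stratifying the log-rank comparisons by the same factor would be consistent with the design, but its gain is unquantified and it should be presented as optional.

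The cost is one clause once the stratum is defined, and one degree of freedom per model: about 0.1% in interval width by simulation, or 1% by the formula, if grade adds nothing. The planned 54 does not change, and glioma grade is already collected at screening. The change is best made before outcome data are seen.
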